#### Rituximab maintenance group

Rituximab 1000 mg x 1 dose at months 4, 8, 12, 16 and 20 and glucocorticoids.

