## 11.6 Treatment of relapse

Patients experiencing their first minor relapse after randomisation and before month 24 of the treatment phase will remain on the randomised treatment (rituximab or azathioprine) and will have their oral prednisolone/prednisone increased to 20mg/day for one week decreasing in 2.5mg increments each week to reach 5mg/day after six weeks. The second minor relapse or first major relapse, occurring before month 24 of the treatment phase will result in the patient being withdrawn from protocolised treatment and returned to treatment according to local best practice. Any relapse occurring after the 24 month treatment phase will be treated according to local best medical practice.

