## 5. Treatment Exposure (Treatment Form)

---

 A different scoring system from the one used in the Induction phase report is employed. This new scoring system is based on COMBIVAS's VDI (Vasculitis Damage Index) form. The new scoring system has a maximum score of 64, compared to the Induction phase report one that had a maximum score of 110. For comparison new CDA scores for the Induction phase months (visits Month 0 and Month 4) will be included in this report. Further details on how the CDA score is computed can be found in section 9.8.

- **Total maintenance rituximab dose (mg)** – cumulative rituximab dose across the maintenance phase of treatment only, from the Treatment Form of months 4, 8, 12, 16 and 20. Missing data (due to early withdrawal or any other reason –e.g. missing form) will be ignored (i.e. it's assumed no treatment was given, 0 mg).
- **Overall full rituximab treatment – maintenance (Yes/No)** – categorical variable, determining whether the subject has received all five full rituximab infusions as per protocol. Subjects are assumed to have followed protocol unless deviations were explicitly recorded in the Treatment form (i.e. "Treat6" = 1), any recorded deviation is considered an overall non-compliance, while missing forms are ignored.
- **Number of full rituximab infusions administered (integer)** – calculated across the maintenance phase of treatment, from the Treatment form of month 4,8,12,16 and 20. Counts explicitly the number of months when rituximab treatment was administered according to protocol. Thus "3 doses" would mean that 3 infusions administered were given as per protocol. Missing forms (NA) are ignored.
- **Total maintenance IV methylpredniso(lo)ne dose (mg)** – cumulative IV methylpredniso(lo)ne dose across the maintenance phase of treatment only, from the Treatment form. Missing data (due to early withdrawal or any other reason –e.g. missing form) will be ignored (i.e. it's assumed no treatment was give, 0 mg).

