**Table 5: ANCA Status**

		Anti-MPO		
		Positive	Negative	Not measured
Anti-PR3	Positive	Positive PR3 & MPO	Positive PR3	Positive PR3
	Negative	Positive MPO	Negative	Unknown
	Not measured	Positive MPO	Unknown	Unknown

Table 6: Details of formulas for derived variables

Variable name	Label	Type	Original variables (MACRO ShortCode)	Formula
MHDuration	Prior disease duration	Real	MHDat1, Visit1	Date difference (years)
HisANCA	Historical ANCA positivity	Category	MHEli1, MHEli2	See Table 4 for details
BLM_Score BLM_Score_cat	Total number of Body Systems affected	Integer/ Category	BLM_* variables	Sum
MHCycl	Total cyclophosphamide	Category	MHTre3, MHTre4	if either = 1 then => 1 (Yes) else => 0 (No)
MHCyclDose	Cumulative cyclophosphamide dose	Real	MHCyc1, MHIVC1	Sum
MHRitCyc	Previous treatment with rituximab or cyclophosphamide (either IV or oral)	Category	MHTre5, MHCycl	if either = 1 then => 1 (Yes) else => 0 (No)
MHImmN MHImmN_cat	Number of prior immunosuppressants	Integer/ Category	CumCyclo, MHTre5, MHTre6, MHTre7, MHTre8, MHTre11, MHTre12, MHImS1, MHImS2, MHImS3, MHImS4, MHImS5, MHImS6	Sum
BVASStatus	Disease status	Category	BVAS12a, BVAS12b, BVAS12c, BVAS12d	Hierarchical order, categories evaluated in order, from the most specific to the most general: 1. Remission 2. Severe flare 3. Limited flare 4. Persistent
CDAScore CDAScore_cat CDAScore_grp	Total CDA score	Integer/ Category	selected variables of CDA Form (see section 9.8)	Sum
CDADiff CDADiff_cat	Change in total CDA score between month 4 and month 12, month 24, month 36 & month 48. Change in total CDA score between	Integer/ Category	CDAScore	Difference

	month 24 and month 36 & month 48			
TreatRituxSum	Total rituximab dose (mg)	Real	TreatTotalRitux	Sum
TreatRituxPrctcol	Overall full rituximab treatment	Category	TreatAdmnProtcol	Yes if sum(TreatAdminProtocol="Yes")=5
TreatRituxMonths	Number of full rituximab infusions	Integer/Category	TreatAdmnProtcol	count(TreatAdminProtocol="Yes")
TreatMPredDose	Total IV methylpredniso(lo)ne dose (mg)	Real	TreatMPredDose	Sum
PredMean PredMean24	Average predniso(lo)ne dose (mg/day) - (Overall /Maintenance)	Real	FUp1aPredDose	Average If FUp1a1 then Fu1aPredDose=0
PredAUC PredAUC24	AUC of predniso(lo)ne dose (mg) - (Overall /Maintenance)	Real	FUp1aPredDose	Vertical step function, assumes month=30days

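### SAP 9.2 gives the variable for completing all five maintenance rituximab infusions two incompatible rules, and the text rule can class a patient who stopped early as complete

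*SAP*

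**What the plan says.** The protocol's maintenance schedule for the experimental arm is "Rituximab 1000 mg x 1 dose at months 4, 8, 12, 16 and 20 and glucocorticoids" (Protocol 11.1.1), so a full course is five infusions and 5000 mg.

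SAP section 9.2, item 5 (Treatment Form), derives a Yes/No variable called Overall full rituximab treatment. Its stated purpose is "determining whether the subject has received all five full rituximab infusions as per protocol". The rule that follows is "Subjects are assumed to have followed protocol unless deviations were explicitly recorded in the Treatment form", and then "any recorded deviation is considered an overall non-compliance, while missing forms are ignored".

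Table 6 of the SAP lists the formulas for the derived variables. Its entry for the same variable (TreatRituxPrctcol) is "Yes if sum(TreatAdminProtocol='Yes')=5".

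Two neighbouring variables in item 5 use the same forms. For total maintenance dose: "Missing data (due to early withdrawal or any other reason –e.g. missing form) will be ignored (i.e. it's assumed no treatment was given, 0 mg". For the number of full infusions: "Counts explicitly the number of months when rituximab treatment was administered according to protocol". SAP 9.10.1 reports all three variables, using the full analysis population.

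**The concern.** The text rule does not measure what the variable is defined to measure. It starts from Yes and moves to No only when a deviation has been written down. A patient who leaves after two or three clean infusions and generates no further Treatment Forms has nothing recorded against them and stays Yes.

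Early stopping is part of the design. A second minor relapse or a first major relapse before month 24 "will result in the patient being withdrawn from protocolised treatment and returned to treatment according to local best practice" (Protocol 11.6), and treatment may also be stopped for medical reasons (Protocol 10.6). After complete withdrawal from the trial no further data are collected (SAP 9.1.2), so in that case the later forms must be missing.

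At stake is the reported proportion of rituximab patients who completed the maintenance course. A reader uses it to judge how well the experimental regimen was delivered. If the programmer follows the text, that proportion can be too high; if the programmer follows Table 6, it is not. The SAP does not say which rule governs.

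**Working it through.** The plan states no figure for this variable, so there is none to reproduce. The check applies both rules to the same data.

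**Inputs.** Five scheduled infusions of 1000 mg (Protocol 11.1.1). Each of the five Treatment Forms is in one of three states: given per protocol, deviation recorded, or form missing.
- Text rule (SAP 9.2, item 5): No if any form records a deviation, otherwise Yes.
- Table 6 rule: Yes only if all five forms are Yes, otherwise No.

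**Patients with *k* clean infusions and no forms afterwards:**

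| Clean infusions | Text rule | Table 6 | Infusion count | Total dose (mg) |
|---|---|---|---|---|
| 0 | Yes | No | 0 | 0 |
| 1 | Yes | No | 1 | 1000 |
| 2 | Yes | No | 2 | 2000 |
| 3 | Yes | No | 3 | 3000 |
| 4 | Yes | No | 4 | 4000 |
| 5 | Yes | Yes | 5 | 5000 |

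The Table 6 result agrees with the infusion count and the total dose in every row. The text rule agrees with them only in the last.

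**All patterns.** There are 3^5 = 243 patterns of five forms. The text rule gives Yes whenever no deviation is recorded, which is 2^5 = 32 patterns. Table 6 gives Yes in one of these, five clean forms. The rules therefore disagree in 32 − 1 = 31 patterns: exactly those with at least one missing form and no recorded deviation. In all 31 the text says Yes and Table 6 says No. The disagreement runs in one direction only. The 31 is a count of patterns; it says nothing about how often they occur.

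**Missing values in Table 6.** The formula does not say what happens when a form is missing. The analysis is to be run in R (SAP section 15). If a missing form is stored as NA and missing values are not removed, the sum returns NA and the patient is neither Yes nor No. The Table 6 rule gives No only if a missing form is made to count as not Yes.

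**Azathioprine arm.** SAP 9.10.1 uses the full analysis population, which includes both arms (SAP 8.2.2). Read literally, the text rule would class an azathioprine patient with no Treatment Forms as having had full rituximab treatment.

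**The case against.** **Table 6 is already right.** It is the formula table, and if it is what gets programmed, no one is misclassified. That is fair: the documents show two rules for one variable, not that the wrong one will be run. But item 5 is where the variable is defined, and nothing ranks one rule above the other.

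**Ignored may mean not counted towards five.** In the dose and infusion-count variables, ignoring a missing form does mean that it adds nothing. Read that way, the text would match Table 6. The sentence does not support this: it presumes adherence by default and sets missing forms against recorded deviations, which are what produce a No. Even if the text is only ambiguous, it still has to be reconciled with Table 6.

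**Forms may exist after early stopping.** The protocol's schedule of events keeps withdrawn subjects on the visit schedule, and the Data Manager routinely queries missing forms (SAP 6.4). A returned form that records a deviation gives No under both rules. This stands, and it is why the conclusion is that an early stopper can be misclassified, not that every one will be.

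**The inconsistency would be visible.** SAP 9.10.1 also reports dose and adherence at each visit, the reasons for non-compliance, total dose and number of full infusions. This largely stands, and it limits the harm.

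**A reader might infer a size from the sample-size assumptions.** With 80 patients per arm, constant hazards and 16 months between the first and last maintenance infusion, 80 × (1 − 0.75^(16/48)) = 7.3 relapses and 80 × (1 − 0.95^(16/24)) = 2.7 drop-outs, about 10 of 80. The documents do not support using this as an estimate or as an upper bound. It treats every relapse and drop-out as lost forms, although a first minor relapse stays on randomised treatment and other patients may have forms returned. It also leaves out stops for toxicity, deaths, and forms missing for any other reason.

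**Conclusion.** The concern holds as an internal contradiction. One derived variable has two rules that give different answers whenever at least one Treatment Form is missing and no deviation is recorded. In each such case the text rule gives Yes for a patient without five documented infusions, so any resulting error overstates delivery of the rituximab regimen.

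The consequence is minor. It is confined to the descriptive exposure summary in SAP 9.10.1. A reader might infer that the trial's efficacy conclusions are affected; they are not. The primary Cox analysis uses the full analysis population as randomised (SAP 8.2.2 and section 10), and membership of the per-protocol populations is adjudicated patient by patient from the Treatment, Follow-Up and Relapse Forms (SAP 8.2.3), not from this variable.

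The number of patients affected cannot be computed from the documents. The conclusion rests on the ordinary reading of the text rule and on some patients having missing forms with no recorded deviation. The SAP itself anticipates missing forms when it names early withdrawal as a reason for missing Treatment Form data.

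**What to change.** In SAP 9.2, item 5:

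1. Delete the sentence that presumes adherence and disregards missing forms.
2. Make the Table 6 rule the only definition: Yes requires five recorded Yes values.
3. State that a missing form counts as not Yes, with missing values removed from the sum, so that the result is No and not NA.
4. Report the variable for patients randomised to rituximab only.

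The text, the formula, the infusion count and the total dose will then agree for every patient. The cost is SAP wording and a check that the program follows it. No data collection, sample size or efficacy analysis changes.

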#### 6. Treatment exposure (Follow Up Form)

- **Average predniso(lo)ne dose (mg/day)** – average predniso(lo)ne dose, from randomisation to the end of trial, using the most recent daily dose as recorded in the Follow Up form at month 4, 8, 12, 16, 20, 24, 27, 30, 36, 42, and 48. If predniso(lo)ne treatment was explicitly recorded as not given in the Follow Up Form (i.e. FUp1a1 = "No") then a dose = 0 mg/day will be implied, while missing data (due to early withdrawal or any other reason –e.g. missing form) will be ignored.

---

 A separate variable in the Follow Up form reports cumulative rituximab dose at 24 months, which includes doses administered during the induction phase.

 A separate variable in the Follow Up form reports cumulative IV methylpredniso(lo)ne dose at 24 months, which includes doses administered during the induction phase

- **Average predniso(lo)ne dose (mg/day) in the maintenance phase** – as above but calculated using the most recent daily dose as recorded in the Follow Up form at month 4, 8, 12, 16, 20, and 24 only.
- **AUC of predniso(lo)ne dose (mg)** – Area under the curve of predniso(lo)ne dose, calculated using the most recent daily dose as recorded in the Follow Up form at month 4, 8, 12, 16, 20, 24, 27, 30, 36, 42, and 48 employing a vertical step function and assuming a month to be 30 days. Missing data will be assumed to have a value of 0 mg/day.
- **AUC of predniso(lo)ne dose (mg) in the maintenance phase** – as above but calculated using the most recent daily dose as recorded in the Follow Up form at month 4, 8, 12, 16, 20, and 24 only.
- **Average azathioprine dose (mg/day)** – average azathioprine dose, from randomisation to the end of trial, using the most recent daily dose as recorded in the Follow Up form at month 4, 8, 12, 16, 20, 24, 27, 30, 36, 42, and 48. Missing data (due to early withdrawal or any other reason – e.g. missing form) will be ignored.
- **Average azathioprine dose (mg/day) in the maintenance phase** – as above but calculated using the most recent daily dose as recorded in the Follow Up form at month 4, 8, 12, 16, 20, and 24 only.
- **Average methotrexate dose (mg/week)** – average methotrexate dose, from randomisation to the end of trial, using the most recent daily dose as recorded in the Follow Up form at month 4, 8, 12, 16, 20, 24, 27, 30, 36, 42, and 48. Missing data (due to early withdrawal or any other reason –e.g. missing form) will be ignored.
- **Average methotrexate dose (mg/week) in the maintenance phase** – as above but calculated using the most recent daily dose as recorded in the Follow Up form at month 4, 8, 12, 16, 20, and 24 only.
- **Average mycophenolate mofetil dose (mg/week)** – average mycophenolate mofetil dose, from randomisation to the end of trial, using the most recent daily dose as recorded in the Follow Up form at month 4, 8, 12, 16, 20, 24, 27, 30, 36, 42, and 48. Missing data (due to early withdrawal or any other reason –e.g. missing form) will be ignored.
- **Average mycophenolate mofetil dose (mg/week) in the maintenance phase** – as above but calculated using the most recent daily dose as recorded in the Follow Up form at month 4, 8, 12, 16, 20, and 24 only.

- **Number of oral immunosuppressants (azathioprine, methotrexate and mycophenolate mofetil) (integer)** – counts the number of treatments of oral immunosuppressants (either azathioprine, methotrexate and mycophenolate mofetil) administered per patient at each visit, during the maintenance phase and overall (from randomisation to the end of trial). Missing data will be ignored.

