#### Glucocorticoids in Maintenance:

A GC dose of 10 mg/day or less is a requirement for randomisation. GC reduces to 5 mg/day by month 6, according to schedule 2, and continues at 5 mg daily until month 16. GC dose is then reduced to 2.5mg/day and completely withdrawn at month 20.

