#### **Schedule 2:**

Week	Maintenance Schedule Daily prednisone dose (mg)
12	10
14	10
16 (randomisation)	10
18	7.5
20	7.5
22	5
24	5

Alternate day dosing regimens (i.e. those that use two different doses on alternate days) may be used to achieve the appropriate average daily dose required by the protocol but differences in alternative day doses may not be >5 mg. For example, a dose of 7.5 mg/day may be achieved by alternating daily doses of 10 mg/day and 5 mg/day.

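### PredMean is an unweighted mean over unequally spaced visits and overstates a compliant patient's end-of-trial prednisolone dose by about 6 to 51%, depending on length of follow-up and on which dose the form records

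*SAP*

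**What the plan says.** SAP 9.2 item 6 defines the variable as "average predniso(lo)ne dose, from randomisation to the end of trial, using the most recent daily dose as recorded in the Follow Up form". It takes the dose from the "Follow Up form at month 4, 8, 12, 16, 20, 24, 27, 30, 36, 42, and 48" for the overall average (PredMean) and from the "Follow Up form at month 4, 8, 12, 16, 20, and 24 only" for the maintenance average (PredMean24). Missing visits are ignored, and a dose of 0 is implied where prednisolone is explicitly recorded as not given (FUp1a1 = No). Table 6 gives the formula as "Average If FUp1a1 then Fu1aPredDose=0". Neither place mentions time weights.

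The same item defines an AUC of prednisolone dose by a vertical step function with 30-day months and missing doses set to 0. It does not say whether a visit's dose is carried forward or backward. SAP 9.10.2 reports the average and the AUC together. They are the oral steroid summaries closest to secondary endpoint 5, cumulative GC exposure.

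The taper is in Protocol 11.5.1. "A GC dose of 10 mg/day or less is a requirement for randomisation", and Schedule 2 shows 10 mg at week 16, 7.5 mg at weeks 18 and 20, and 5 mg from week 22. The dose "continues at 5 mg daily until month 16", is then 2.5 mg, and stops at month 20.

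**The concern.** A mean reported in mg/day should weight each dose by the time it was taken. Here each visit has equal weight although it may stand for 3, 4 or 6 months, so the long steroid-free intervals after month 30 count too little. The month 4 dose adds to this: 10 mg/day held for no more than about two weeks makes up one sixth of the maintenance average and one eleventh of the 48-month average. The result would be read as a typical daily exposure after randomisation and compared with other trials or with the protocol taper.

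**Working it through.** The plan states no value for this average, so there is no figure to reproduce. The check takes a fully compliant patient and compares the SAP rule with the dose actually taken.

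**Inputs.** Taper: Protocol 11.5.1 and Schedule 2. Visits: SAP 9.2. Month length: 365.25/12 = 30.4375 days (SAP 9.1.1). Closing visit: month 36, 42 or 48.

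**True dose** = sum of (dose × days) / days from the month 4 visit to the last visit. The documents use both week 16 and month 4 for randomisation, so three placements were tried:

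- A. Month 4 by calendar (day 121.75), taper by study week: 10×4.25 + 7.5×28 + 5×333 + 2.5×121.75 = 2,222 mg.
- B. Month 4 visit taken as week 16 of the taper: 10×14 + 7.5×28 + 5×323.25 + 2.5×121.75 = 2,271 mg.
- C. Month 4 visit on day 112, later visits by calendar: 10×14 + 7.5×28 + 5×333 + 2.5×121.75 = 2,319 mg.

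To months 24, 36, 42 and 48 the days are 608.75, 974, 1,156.6 and 1,339.25 for A and B, and 9.75 more for C.

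**SAP rule** = sum of visit doses / number of visits (6, 9, 10 or 11). The documents do not say which dose is recorded at months 16 and 20, so both are shown:

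- Dose taken up to the visit: 10, 5, 5, 5, 2.5, 0, … sum 27.5.
- Newly reduced dose: 10, 5, 5, 2.5, 0, 0, … sum 22.5.

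| Last visit | True mg/day (A / B / C) | SAP mean, prior dose | Excess | SAP mean, new dose | Excess |
|---|---|---|---|---|---|
| 24 | 3.65 / 3.73 / 3.75 | 27.5/6 = 4.58 | +22 to +26% | 22.5/6 = 3.75 | 0 to +3% |
| 36 | 2.28 / 2.33 / 2.36 | 27.5/9 = 3.06 | +30 to +34% | 22.5/9 = 2.50 | +6 to +10% |
| 42 | 1.92 / 1.96 / 1.99 | 27.5/10 = 2.75 | +38 to +43% | 22.5/10 = 2.25 | +13 to +17% |
| 48 | 1.66 / 1.70 / 1.72 | 27.5/11 = 2.50 | +45 to +51% | 22.5/11 = 2.05 | +19 to +23% |

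**Source of the excess.** With prior-dose recording, leaving month 4 out of the plain mean gives 17.5/5 = 3.50 to month 24 (4 to 7% low) and 17.5/10 = 1.75 to month 48 (2 to 5% high). Month 4 is therefore the main cause. Unequal spacing matters only after month 24, because the maintenance visits are evenly spaced.

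**Candidate remedies**, in mg-months to month 24 with 4-month intervals. Later doses are 0, so the percentages hold at every closing visit; the ranges cover A to C.

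- Backward weights, month 4 left out. Prior dose: 4×(5+5+5+2.5+0) = 70, or 3.50 mg/day, 4 to 6% low. New dose: 4×(5+5+2.5+0+0) = 50, or 2.50 mg/day, 32 to 33% low.
- Trapezoidal, month 4 included. New dose: 4×(7.5+5+3.75+1.25+0) = 70, or 3.50 mg/day, 4 to 6% low. Prior dose: 4×(7.5+5+5+3.75+1.25) = 90, or 4.50 mg/day, 21 to 23% high.

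**The AUC as defined**, prior dose, 30-day months. Carried forward: 4×27.5×30 = 3,300 mg against 2,222 to 2,319 mg (42 to 49% high). Carried backward: 4×17.5×30 = 2,100 mg (5 to 9% low).

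**The case against.** Four points can be made in the plan's defence.

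- **The size is conditional.** A reader might infer a flat overstatement of 25 to 50%. That needs the pre-reduction dose to be recorded at months 16 and 20. The words on the most recent daily dose lean that way but do not settle it, and the form is not in the documents. Under the other reading the maintenance average is nearly exact. This stands.
- **No bias between arms is shown.** A reader might infer that the arms are compared on different scales, especially where relapses raise the steroid dose at different times. Both arms share the taper and visits, so compliant patients show no differential error. The relapse argument turns on the carry direction. An extra 10 mg/day recorded at months 27 and 30 counts as 20/11 = 1.82 under the SAP rule, against 60/44 = 1.36 carried backward but 90/44 = 2.05 carried forward, so the sign of the error reverses. This stands.
- **A time-based measure already exists.** The AUC is closer to the endpoint, and SAP 9.2 and 9.10.2 specify no test of steroid exposure. That limits the consequence. It does not make PredMean correct, and the AUC's own result depends on a step direction that the SAP leaves open.
- **Table 6 is shorthand.** The cell reads "If FUp1a1 then Fu1aPredDose=0", and a reader might infer that treated patients will be set to 0. The text of 9.2 gives the condition in full, so nothing shows that the code will do this. It is an editorial mismatch.

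The 10 mg is also not purely an induction dose: Schedule 2 is the maintenance schedule and lists it at the randomisation week. The fault is the weight it receives.

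**Conclusion.** The concern holds in a limited form. PredMean is not a time-weighted daily dose, and for a fully compliant patient it is too high at every closing visit under both recording conventions and all three placements of month 4: about 6 to 34% at month 36 and 19 to 51% at month 48. PredMean24 is about 22 to 26% too high if the prior dose is recorded and 0 to 3% if the new dose is. The figures assume exact adherence to Schedule 2 and no missing visits. The error concerns the absolute level of a descriptive summary serving a secondary endpoint. The primary analysis is untouched, and the documents do not support a claim of bias between arms.

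**What to change.** 1. State in SAP 9.2 whether the Follow Up form records the dose taken up to the visit or the new dose on a day when the dose changes. This comes first, because the right weighting depends on it.
2. Define PredMean and PredMean24 as the area under the dose curve divided by the days from the month 4 visit to the last visit.
   - If the form records the dose taken up to the visit, weight each dose from month 8 on by the days since the previous visit and leave out month 4.
   - If it records the new dose, or this cannot be established, use trapezoidal weighting between visits with month 4 included. For the new dose this is 4 to 6% low. If the prior dose was in fact recorded it is 21 to 23% high, against 45 to 51% for the plain mean at month 48. For PredMean24 it brings little or no gain over the plain mean, which is a further reason to settle step 1.
3. Write the same step rule into the AUC definition.
4. Align the Table 6 cell with the text: dose = 0 only if FUp1a1 = No.

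The cost is a few sentences in the SAP, one table correction and a small code change. No new data are needed.
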